#### SCHEMA

Dosing schedule for uproleselan and standard conditioning

# **OBJECTIVES**

#### 1.1 Hypothesis

The long range hypothesis of this project is that incorporating uproleselan into pre-transplant conditioning for acute myeloid leukemia will decrease post-transplant relapse and improve leukemia free survival.

#### 1.2 Study Design

Single arm, multi-center, phase 1/2 trial.

# **1.3 Primary Objectives**

Phase 1. To assess the safety and tolerability and identify the recommended phase 2 dose (RP2D) of uproleselan when combined with myeloablative, busulfan-based, pre-transplant conditioning regimens for treatment of acute myeloid leukemia.

Phase 2. To describe the safety of uproleselan at the RP2D when combined with myeloablative, busulfan-based, pre-transplant conditioning regimens for treatment of acute myeloid leukemia.

#### 1.4 Secondary Objectives

- 1) To describe the pharmacokinetics of uproleselan in pediatric patients receiving myeloablative, busulfan based pre-transplant conditioning (this will encompass both phase 1 and phase 2).
- 2) To describe the preliminary efficacy of uproleselan by estimating the 12-month leukemia-free survival (LFS), overall survival (OS), and relapse in patients receiving uproleselan at the RP2D
- 3) To describe the maximal severity of oral and gastrointestinal mucositis in patients receiving uproleselan at the RP2D.

# **1.5 Exploratory Objectives**

These preliminary assessments will be performed to prepare for more definitive assessments in a full scale clinical trial.

- 1) To obtain preliminary data on AML blast E-selectin ligand (EsL) expression by multidimensional flow cytometry as predictor of uproleselan response.
- 2) To obtain preliminary data on AML transcript expression of the EsL related glycan synthesis genes ST3GAL4 and FUT7.

# 2. BACKGROUND

# 2.1 IND Agent: Uproleselan

E-selectin is constitutively expressed on the sinusoidal endothelial cells of the marrow's vascular niche and plays a critical role in the regulation of hematopoietic stem cell quiescence, self-renewal, activation and homing. AML cells hijack the vascular niche through secretion of TNF $\alpha$  and other inflammatory mediators, increasing endothelial expression of E-selection, and through alterations in the E-selectin ligand, augmenting their E-selectin binding potential. E-selectin activates pro-survival signaling in AML cells through AKT/NF-kB pathways. This protects AML leukemia regenerating cells from cytotoxic chemotherapy. Uproleselan, a small molecule E-selectin mimetic, blocks this interaction, abrogating pro-survival signaling and, thereby, sensitizing AML cells to chemotherapy.

A phase I/II trial combining uproleselan with conventional chemotherapy for treatment of adults with AML has been completed (ClinicalTrials.gov identifier: NCT02306291). In the phase I portion, patients  $\geq$ 18 years with relapsed or refractory disease were enrolled and received uproleselan combined with mitoxantrone, etoposide and cytarabine (MEC) as induction therapy. Three dose levels (5 mg/kg, 10 mg/kg, and 20 mg/kg bid IV) were assessed, and no dose limiting toxicities were identified. 10 mg/kg was selected as the dose for phase II assessment based on the pharmacokinetic and pharmacodynamic assessments. The phase II portion involved two strata: one for patients  $\geq$ 18 years with relapsed or refractory disease who received uproleselan combined with MEC for induction (patients achieving remission could receive a second course as consolidation) ); and a second stratum for patients  $\geq$ 60 years with newly diagnosed AML who received uproleselan combined with daunomycin and cytarabine ("7+3") as induction (patients achieving remission could receive a second with idarubicin and cytarabine).

Severe ( $\geq$  grade 3) non-hematologic adverse events were uncommon; the incidences of oral mucositis, intestinal mucositis and blood stream infections were low and consistent with what would be expected for adult AML patients receiving intensive chemotherapy. The induction mortality rate was low for both the relapsed refractory and the newly diagnosed cohort. There were no DLT's attributed to uproleselan. For subjects who received uproleselan (any dose level) plus MEC, 23/66 (35%) experienced at least 1 CTCAE Grade 3 or 4 treatment emergent adverse event (TEAE) assessed to be related to uproleselan. A total of 8/25 subjects (32%) who received uproleselan 10 mg/kg plus 7+3 experienced at least 1 related CTCAE Grade 3 or 4 TEAE assessed to be related to uproleselan. The most frequently reported CTCAE Grade 3 or 4 TEAEs assessed to be related to uproleselan for subjects who received uproleselan (any dose level) plus MEC were febrile neutropenia (11/66 subjects; 17%), thrombocytopenia (7/66; 11%), anemia (5/66; 8%), neutropenia (3/66; 5%), sepsis (3/66; 5%), and platelet count decreased (4/66 subjects; 6%). The most frequently reported CTCAE Grade 3 or 4 TEAEs assessed to be related to uproleselan for subjects who received uproleselan 10 mg/kg plus 7+3 were febrile neutropenia (3/25 subjects; 12%), thrombocytopenia (3/25; 12%), anemia (2/25; 8%), and pneumonia (2/25 subjects; 8%). Durable high remission rates were achieved in both groups. The complete

remission/complete remission with incomplete hematologic recovery (CR/CRi) rate was 41% (27/66 subjects) for subjects who received uproleselan (any dose level) plus MEC and 43% (23/54 subjects) for subjects who received the RP2D uproleselan 10 mg/kg plus MEC. For patients receiving "7+3" the CR/CRi was 68% (17/25). Overall survival was also encouraging in both groups. The median OS was 8.8 months (range 0.9 - 28.8 months) for participants who received the RP2D uproleselan 10 mg/kg plus MEC and 8.8 months (range 0.1 - 22.0 months) for participants who received uproleselan 10 mg/kg plus 7+3. Correlative studies yielded two important findings: one, that E-selectin ligand is detectable on blasts of all patients; two, that the proportion of functional E-selectin binding by circulating blasts is associated with the achievement of remission and survival.

This trial's encouraging results paved the way for two full scale clinical trials: a phase II/III RCT of daunomycin and cytarabine induction +/- uproleselan in older adults with newly diagnosed AML being conducted by the NCI and led by the Alliance (ClinicalTrials.gov identifier: NCT03701308); and a phase III RCT of MEC or fludarabine, cytarabine and idarubicin (FAI) +/- uproleselan in adults with relapsed or refractory AML being conducted by GlycoMimetics, Inc. (ClinicalTrials.gov identifier: NCT03616470). In these trials, a fixed dose of 800 mg of uproleselan is being used to provide an exposure approximating the weight-based dose of 10 mg/kg. In the Phase I/II study, the RP2D dose was 10 mg/kg, and subjects had a median weight of 81.3 kg. The results of the population PK analysis suggest that clearance does not vary with body size. As a result, a fixed dose, rather than a weight-adjusted dose is likely to minimize between-subject variability. Combining the RP2D and median weight with the lack of body size as a covariate, suggests that a fixed dose of 800 mg would provide equivalent exposure as the RP2D (10 mg/kg) ([name], GlycoMimetics, Inc.-personal communication, January, 2020).

2.1.1 Uproleselan's potential to decrease transplant-related mortality and morbidity by reducing mucositis.

As noted above, in the phase 1/2 trial of uproleselan combined with intensive AML chemotherapy, the incidences of severe oral and intestinal mucositis were low. Uproleselan has been shown to diminish oral and intestinal mucosal barrier injury following high dose chemotherapy or total body irradiation in mice. Mechanistic studies indicate that this is due to inhibition of E-selectin mediated migration of macrophages to sites of cytotoxic mucosal injury, thereby, abrogating mucosal inflammation. Protection against mucosal barrier injury could yield two additional benefits in the setting of allogeneic HSCT. First, it could mitigate bacterial translocation, decreasing the risk for blood stream infections. Notably, the incidence of bacteremia in the phase 1/2 trial was low. Second, protection against mucosal barrier injury could lessen the risk for acute graft-versus-host disease (GVHD), since gastrointestinal mucosal injury plays a central role in the pathogenesis of acute GVHD.

2.1.2 Protection of normal hematopoietic stem cells from the cytotoxic effects of chemotherapy by uproleselan

In murine models, the effects of uproleselan on normal hematopoietic stem cells and leukemia cells are divergent. Rather than sensitizing normal hematopoietic stem cells to the cytotoxic effects of chemotherapy, it protects them. With conventional chemotherapy treatment, uproleselan accelerates neutrophil recovery, providing another mechanism by which uproleselan could prevent mucositis and blood stream infections. In the setting of allogeneic HSCT, uproleselan's protection of normal hematopoietic stem cells could be disadvantageous. By protecting host hematopoietic stem cells from the effects of conditioning, uproleselan could hinder donor hematopoietic stem cell engraftment. However, according to recent experiments conducted by GlycoMimetics, Inc. the protective effect of uproleselan on normal hematopoietic stem cells may not be sufficient to impede donor engraftment. In a murine congenic transplant model, uproleselan administered prior to myeloablative total body irradiation did not alter engraftment.

2.1.3 Justification for dose levels and pharmacokinetic assessment

Previous trials in adult patients have provided a robust pharmacokinetic (PK) dataset for use in population PK modeling, which allows simulation of dose levels and subsequent exposure across different weight and age groups. Doses from 2 to 40 mg/kg were assessed in adults, in both healthy volunteer and patient trials. Minimal accumulation of uproleselan at any dose level was observed, as expected from its short half-life. The PK optimal model was a three-compartment model that included a time-lagged input and the effect of renal function (as estimated by creatinine clearance, using the Cockcroft-Gault equation) on clearance. Clearance of uproleselan varies with renal function and does not vary with body size or any other covariate evaluated in the adult population (50-150kg).

Since this trial is the first in children and the first in hematopoietic stem cell transplantation (HSCT), dosing will start at 10 mg/kg/dose q12H and will not be escalated. It includes a provision for de-escalation to 5 mg/kg/dose q 12 H, if the starting dose is not well tolerated. PK data obtained from this trial will be assessed using a population PK model. to determine actual exposure and coefficient of variation in children and adolescents . These results will inform uproleselan in future pediatric trials.

# 2.2 Relapse after HSCT for AML

Recurrence of disease represents the most important cause of treatment failure after allogeneic hematopoietic stem cell transplantation (HSCT) for patients with acute myeloid leukemia (AML). Most relapses occur in the first year after transplant and durable remissions after relapse are rare. Hence, prevention of relapse represents a major focus of research. In the Second Annual International Cancer Institute's Workshop on the Biology, Prevention and Treatment of Relapse after HSCT, the incorporation of novel agents into pre-transplant conditioning regimens to enhance their anti-leukemic effect was proposed as one of the key strategies to be explored for relapse prevention.

# 2.3 Incorporating Uproleselan into Busulfan Conditioning to Enhance its Anti-leukemic Effect

In this trial, uproleselan will be combined with the busulfan, fludarabine and clofarabine regimen, a regimen developed from the standard busulfan and fludarabine regimen commonly employed for both adults and children with AML. Building on pre-clinical research demonstrating that the newer purine analogue clofarabine possesses greater activity against AML than fludarabine, and that clofarabine's activity can be enhanced by low doses of fludarabine, investigators at MD Anderson have conducted two randomized controlled trials to assess the effects of combining fludarabine and clofarabine with busulfan. In the first, an early phase trial in adults with AML or MDS, they examined varying dose combinations of the two purine analogues and identified 10 mg/m2/dose of fludarabine and 30 mg/m2/dose of clofarabine as the optimal combination. In the second, a recently completed phase 3 trial, 250 (median age =51 years, range =3 to 70 years) patients with AML (n=181) or MDS (n=69) receiving HLA matched related or unrelated donor transplants were randomized to receive busulfan with fludarabine (40 mg/m2/dose) or busulfan with fludarabine (10 mg/m2/dose) and clofarabine (30 mg/m2/dose). Preliminary trial results indicate that busulfan-fludarabine-clofarabine's (BFC) is associated with a lower risk of relapse, especially in patients whose disease is not in remission at the time of

admission, but is also associated with a higher risk of non-relapse mortality, especially in patients with multiple pre-existing co-morbidities. As a result for the group as a whole, there were no differences in progression-free or overall survival. In a sub-group analysis of the patients without significant co-morbidity (co-comorbidity index=0-2) and not remission, however, overall survival was significantly higher patients receiving BFC.

Importantly, BFC has been extended to a large group of children and adolescents at the Leiden University Medical Center and University Medical Center Utrecht transplant centers in the Netherlands. 155 children (median age 9.7 years) with hematologic malignancies were enrolled, including 69 with AML (28 in CR1, 40 in CR2, 1 with active disease). 119 patients received transplants from unrelated donor. Most patient received either bone marrow (n=79) or cord blood (n=66) grafts. There were only 2 cases of non-engraftment. Non-relapse mortality at 3 years was 10.3%. No veno-occlusive disease of the liver was observed. The cumulative incidence of relapse in AML was 22.5% and event free survival for patients transplanted in AML in 1st CR and 2nd CR was 64% and 65%, respectively. These results demonstrate that in pediatric patients BFC is safe, well suited for cord blood transplantation and effective for AML.

BFC was chosen for use as the conditioning backbone in this trial because it may be more effective in patients with chemotherapy-resistant AML, because it is safe in pediatric patients and because it is immunosuppressive enough to produce robust engraftment in cord blood transplantation.

The current trial builds on other recent attempts to add novel chemotherapy agents to BF or BFC conditioning in adults with AML. The list of agents that have been tested or are currently being tested in early phase trials includes plerixafor, CPX-35121 and vorinostat (NCT02083250).

# 2.4 Rationale

This phase 1/2 trial will allow us to prepare for a full-scale clinical trial, open to patients with chemo-sensitive as well as chemo-resistant AML and to patients receiving a wider variety of donor/graft types and forms of conditioning and GVHD prophylaxis. We anticipate that in the full-scale clinical trial, patients with chemo-sensitive disease will be assigned to a randomized stratum (uproleselan vs. placebo), while patients with chemo-resistant disease will be non-randomly assigned to treatment with uproleselan.

Eligibility: Eligibility for the trial will be limited to those patients at highest risk for relapse: those transplanted with refractory disease (not in remission) or transplanted in a complete remission, but with measurable residual disease on marrow testing by multidimensional flow cytometry (MRD positive). The risk of relapse associated with pre-transplant MRD approaches that associated with refractory disease. A large analysis of children and adults transplanted for AML in first or second complete remission (CR1 or CR2) showed that patients with any level of MRD pre-transplant had a nearly five-fold higher risk of relapse at 3 years compared to those who were MRD negative. Importantly, pre-transplant MRD obviated the significance of traditional risk factors, including cytogenetic risk and remission number. Similar results were shown in a pediatric only cohort in the Pediatric Blood and Marrow Transplant Consortium study ONC001 for patients receiving allo-HSCT in CR1 or CR2. The 2-year cumulative incidence of

relapse was 32% for the 113 patients who were MRD negative prior to HSCT as compared to 70% for the 10 patients who were MRD pos. (p=0.01). In both of these studies, most of the relapses in patients who had pre-HSCT MRD occurred by 6 months. In both studies, relapse-free survival for MRD positive patients was approximately 40% at 6 months.

# 2.5 Correlative Studies Background

In this trial, we will explore E-selectin related biomarkers. We will assess the proportion of baseline bone marrow blasts with detectable E-selectin ligand (EsL), which could be an important determinant of benefit from uproleselan. The proportion of blast cells expressing EsL could thereby inform eligibility for future trials of uproleselan in HSCT.

In patients not receiving uproleselan, EsL expression has been shown to be associated with poorer prognosis. Investigators from the Children's Oncology Group (COG) examined the prognostic importance of EsL expression in 1074 children, adolescents and young adults with newly diagnosed AML enrolled on the phase 3 AAML1031 trial. They assessed expression with transcriptome analysis of 24 genes involved in glycosylation of EsL. In their transcriptome analysis, they identified 7 genes where expression was associated with increased risk of treatment failure. Of these, they selected two for further analysis, ST3GAL4 and FUT7, as they directly synthesize sLex. Overall survival ranged from 45.8% in patients with high expression (highest quartile) of both genes (SFhigh), to 55.5% in patients with high expression of one gene (SFinter), to 71.0% in patients without high expression of either (SFlow, p<0.0001). These investigators also observed variation in expression of these genes across patient sub-groups. 71.5% of infants <1 year were SFlow, and only 4.66% SFhigh. 97% of patients with core binding factor AML were SFlow and 0% SFhigh. These investigators also performed multidimensional flow cytometry (MDF) to detect cell surface EsL expression and demonstrated that SF gene expression was strongly correlated with EsL surface expression.

A cross-sectional study in adults with AML demonstrated much higher EsL expression by MDF in patients with relapsed/refractory AML than in patients with newly diagnosed AML. Similarly, EsL expression was much higher in patients with unfavorable cytogenetic/molecular abnormalities than those with favorable/intermediate risk markers.

The adverse impact of EsL on prognosis may be negated by uproleselan. In fact, preliminary data from the phase 1/2 trial in adults discussed above suggests that degree of EsL expression may influence response to uproleselan. Data on EsL expression measured by MDF was available at study entry in 36 of 66 patients enrolled. Though EsL was detectable on blasts in all patients, there was great variation. Degree of expression on leukemia stem cells was dichotomized. In 22 patients (61%), the level was  $\geq 10\%$ . In the remaining 14 patients it was < 10 %. In the high expression group, the CR/Cri rate was 45% and median overall survival was 12.7 months. In the low expression group, the response rate was 29% and median survival 5.4 months28. More data is needed to determine if EsL expression can be used to identify patients likely to benefit from uproleselan. In the current trial, pre-transplant marrow samples will be evaluated for EsL expression by gene expression and MDF.

# **3. PARTICIPANT SELECTION**

Once informed consent has been obtained, the investigator may begin screening studies to confirm eligibility. Once all eligibility criteria have been satisfied, the investigator may enroll the participant according to Section 4. All clinical and laboratory studies to determine eligibility must be performed within 28 days prior to enrollment.

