# **Exceptions:**

• Disease staging bone marrow testing, CSF assessment and assessment of other extramedullary disease must be performed within 14 days prior to enrollment.

Start of conditioning must be within 7 days of enrollment.

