# **3.2** Exclusion Criteria

- 3.2.1 Participants who have had a previous hematopoietic stem cell transplantation
- 3.2.2 Participants who have had prior treatment with uproleselan
- 3.2.3 CNS 3 disease at time of admission for HSCT. Patients previously diagnosed CNS 3 disease that has improved (CNS1 or CNS2) will be eligible. (See Section 3.3 for definitions).
- 3.2.4 Down Syndrome
- 3.2.5 Fanconi Anemia, Dyskeratosis Congenita and other disorders associated with excess risk for transplant related toxicities
- 3.2.6 Acute Promyelocytic Leukemia

- 3.2.7 Multiply relapsed ( $\geq 2$ ) disease
- 3.2.8 Pregnancy (positive serum beta-HCG) or breastfeeding Because there is an unknown but potential risk for adverse events in nursing infants secondary to treatment of the mother with uproleselan, breastfeeding should be discontinued if the mother is treated with uproleselan. These potential risks also apply to other agents used in this study.
- 3.2.9 Absolute neutrophil count <300/µL due to treatment (chemotherapy or immunotherapy).

Patients with neutropenia due to disease related marrow dysfunction (refractory disease, underlying myelodysplasia or an underlying marrow failure disorder) will be eligible regardless of the absolute neutrophil count. However, enrolling centers must provide clear evidence that the neutrophil count is not rising, that the patient does not have an inadequately controlled infection (see section 3.2.15), and that the patient is on broad anti-fungal prophylaxis.

Given the serious risk associated with starting conditioning in patients with severe neutropenia, centers are encouraged to delay transplant if they have any reason to believe that the absolute neutrophil count may improve.

- 3.2.10 Estimated GFR of <60 mL/min/1.73 m^2. Estimated GFR may be calculated using the CKD-EPI Creatinine Equation (2009) for patients ≥19 years or creatinine-based Bedside Schwartz equation (2009) for patients <19 years. It is recommended that estimates be determined using the calculators found on the National Kidney Foundation website. the (https://www.kidney.org/professionals/KDOQI/gfr\_calculator). Any patient for whom these equations yields a GFR less than 90 mL/min/1.73 m^2 should have radionucleotide testing. Measurement of 24-hour urine creatinine clearance is not an acceptable substitute for radionucleotide testing.
- 3.2.11 Cardiac ejection fraction <50% or shortening fraction <27%

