# Treatment may not begin without confirmation from the coordinating center that the participant has been registered and enrolled on study.

# 5. TREATMENT PLAN

# 5.1 Treatment Regimen

This is a phase 1/2 trial comprised of a dose-finding phase (phase 1) to determine the RP2D of uproleselan followed by a dose expansion phase (phase 2) to further assess safety and to make a preliminary assessment of efficacy of the RP2D. In both phases, uproleselan will be combined with a high dose busulfan-based myeloablative conditioning regimen (busulfan, fludarabine, and clofarabine) starting with a single dose on day -8, followed by doses q12 hours (H) on conditioning day -7 and ending on day -2 (Table 1).

Table 1. Pre-transplant Conditioning				
Uproleselan with Busu	Uproleselan with Busulfan, Fludarabine, Clofarabine			
Days -8 to day -2	
 
Uproleselan will be administered IV over 20 minutes (+/- 2 minutes) per assigned dose level in the phase 1 portion or at the RP2D in the phase 2 portion. The maximum dose of uproleselan is 800mg BID. The 20 minute infusion time should include the line flush to ensure the full dose has been infused.
 
A single primer dose will be administered on day -8
 
Beginning on day -7 (with start of fludarabine, clofarabine and busulfan) 12 doses of uproleselan will be administered q 12 H.
 
The 1st, 3rd, 5th, and 7th of theses 12 doses (not including initial day -8 dose) should be administered sequentially, after clofarabine and just prior to busulfan. Delay of doses should be avoided.
 
The last dose of uproleselan will be administered 12 hours (+/- 60 minutes) after dose 11.
 
			
Days –7 to –4	Fludarabine 10 mg/m²/dose daily IV administered as a 30 minute*infusion immediately prior to clofarabineClofarabine 30 mg/m²/dose daily IV administered as a 120 minute*infusion immediately after fludarabine and just prior to uproleselanBusulfan IV daily IV over 3 hours administered immediately afteruproleselan.			
	See section 5.2.1 for details			

	• Busulfan exposure targeted to 80-100 mg x h/L		
Day -1	-1 Rest		
Day 0 Hematopoietic Stem Cell Infusion			
*Duration of infusion may be adjusted nor institutional standards			

\*Duration of infusion may be adjusted per institutional standards

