# 5.2 Agent Administration

Uproleselan will be administered as a 20 minute (+/- 2 minutes) IV infusion (including flush) with dose per assigned level. The maximum dose of uproleselan is 800mg BID. A single priming dose will be administered on Day -8. 12 additional doses will then be administered q 12 H beginning immediately after clofarabine and just before busulfan on Day -7. The dose of uproleselan can be rounded to the nearest whole unit to avoid decimal dosing. Dosing will be based on actual weight. Weight can be collected up to 7 days prior to first dose administration, if weight changes by >10% prior to first dose, dose will be adjusted to current weight. Doses of Uproleselan should not be adjusted once conditioning has started.

Reactions to uproleselan infusions have not been observed to date. Patients should have vital signs just prior to infusion and repeated with the start of the infusion three times at 10-minute (+/- 2 minutes) intervals. Frequent vitals can be discontinued if the patient has not manifested any signs of anaphylaxis or other serious infusion-related reaction. The infusion should be discontinued for any signs of anaphylaxis and the event should be reported immediately to the study team.

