# 10. STUDY CALENDAR AND REQUIRED ROUTINE TESTING/CLINICAL EVALUATIONS

Table 8. Study Calendar						D	ay Relati	ive to Tra	nsplant			
						+30	+50	+100	+180	+365	+730	
Routine Testing and Clinical Evaluations	Baseline a	-8	-4	0	+14	+/- 5 days	+/-7 days	+/- 7 days	+/- 14 days	+/- 30 days	+/- 90 days	InForm Timepoints
Informed consent/assent	X											Baseline
Demographics	X											Baseline
Medical history	X	X										Baseline, Day -8
Physical exam	Xb	X		X		X		X		X	Х	Baseline, Days -8, 0, +30, +100, +365, and +730
Performance status	X	X		X		X		X		X	Х	Baseline, Days -8, 0, +30, +100, +365, and +730
Serum Pregnancy Test	X											Baseline
Estimated GFR	X											Baseline
Echocardiography	X			1								Baseline
Pulmonary Function c	X			1								Baseline
Testing Hep B and Hep C infection	X											Baseline
PK collection d		Х	X									Day +30
E-selectin ligand BM collection d	X											Baseline
Disease re-evaluation e	X					X						Baseline, Day +30
Blood chemistries f	X	Twice weekly through Day +50 Per institutional guidelines				nes	Baseline, Day +30, Day +100					
CBC	X			2			itional gi			0		Baseline, Day +30, Day +100
Coagulation studies	X											Baseline
Urinalysis	X											Baseline
TNC dose, CD3+ and CD34+ counts on infused product				X								Day 0
Peripheral blood chimerism g						X						Day +30
RRT evaluation		D0 - D+30 Daily while inpatient, or 3x weekly if outpatient						Day +30				
MBI-LCBI			D0 - D+30 Daily while inpatient, or 3x weekly if outpatient				Day +30					
VOD/SOS evaluation				D0 while	- D+30 inpatien	Daily t, or 3x						Day +30
Oral and Intestinal Mucositis Evaluation				Dail	y D0 - +14							Day +30
Acute and Chronic GVHD Evaluation				1	Per ins	titutiona	l guidelin	es through	h Day +36	5		All
Relapse and Survival			Pe	er institu				Day +730				All

a. All clinical and laboratory studies to determine eligibility must be performed within 28 days prior to enrollment unless otherwise indicated in Section 3

b. Baseline includes height and weight

c. For patients developmentally unable to perform pulmonary function tests, documentation of oxygen saturation on room air will suffice

d. Refer to Table 7 for timing and other instructions for collection

e. Includes marrow testing and re-assessment of any extramedullary disease, including imaging and/or CSF, as indicated, +/- 5 days from Day +30 assessment

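### The only scheduled pregnancy test may be 34 to 35 days old at the first uproleselan dose and 35 to 36 days old at the first chemotherapy

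*Protocol*

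**What the plan says.** Protocol Section 3 gives the general rule for screening: "All clinical and laboratory studies to determine eligibility must be performed within 28 days prior to enrollment". The exceptions listed under it shorten the window only for staging marrow, CSF and other extramedullary assessment, which "must be performed within 14 days prior to enrollment". The same list adds "Start of conditioning must be within 7 days of enrollment", and Sections 4.1 and 4.3 repeat this 7-day allowance.

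Exclusion 3.2.8 reads "Pregnancy (positive serum beta-HCG) or breastfeeding", so the beta-HCG is an eligibility test and falls under the general rule. In Section 10, Table 8 has a row "Serum Pregnancy Test" marked in the Baseline column only, and its data-capture timepoint is also Baseline only. Footnote a to that column says "All clinical and laboratory studies to determine eligibility must be performed within 28 days prior to enrollment unless otherwise indicated in Section 3". Section 3 does not indicate otherwise for this test.

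On dosing, Section 5.2 states "A single priming dose will be administered on Day -8". Table 1 in Section 5.1 starts busulfan, fludarabine and clofarabine on Day -7. For Day -8, Section 10.1 asks for history, physical examination and performance status, plus the PK samples of Table 7. It lists no pregnancy test.

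**The concern.** The purpose of exclusion 3.2.8 is to keep a pregnant patient from receiving uproleselan and myeloablative conditioning. What matters for that purpose is pregnancy status at the first dose, but the protocol ties the test to enrollment and then allows a further delay. A pregnancy that begins, or becomes detectable, after the test can reach Day -8 unnoticed while every stated rule is met.

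The protocol's own toxicity tables describe the hazard: teratogenic effects of busulfan in animals (7.1.3), possible fetal harm from clofarabine (7.1.4), fetal harm from fludarabine (7.1.5), and human teratogenicity of methotrexate (7.1.7), which Section 5.2.2 plans from Day +1. Elsewhere the protocol does tie facts more closely to treatment: 14 days for disease staging, 7 days before the first dose for weight (5.2), and CNS status at admission for transplant (3.2.3). The pregnancy test has no such rule.

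**Working it through.** The protocol gives no figure for the age of the test at dosing, so there is none to reproduce. The check is day arithmetic.

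**Inputs**
- Eligibility test to enrollment: at most 28 days (Section 3; Table 8 footnote a).
- Enrollment to start of conditioning: at most 7 days (Section 3 exceptions; 4.1; 4.3).
- First uproleselan: Day -8. First chemotherapy: Day -7 (5.1, Table 1; 5.2).
- Scheduled pregnancy tests: one, at Baseline (Table 8).

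**Start of conditioning.** Table 1 places Days -8 to -2 under conditioning, while the text of 5.1 speaks of Day -7 as a conditioning day. Both readings are therefore worked.

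Earliest enrollment = start day - 7. Earliest test = earliest enrollment - 28. Maximum age at a dose = dose day - earliest test day.

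| | Start = Day -8 | Start = Day -7 |
|---|---|---|
| Earliest enrollment | -8 - 7 = Day -15 | -7 - 7 = Day -14 |
| Earliest test | -15 - 28 = Day -43 | -14 - 28 = Day -42 |
| Age at first uproleselan (Day -8) | -8 + 43 = 35 days | -8 + 42 = 34 days |
| Age at first chemotherapy (Day -7) | -7 + 43 = 36 days | -7 + 42 = 35 days |

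**With a 7-day limit counted back from Day -8.** The test is at most 7 days old at Day -8 and 8 at Day -7. The reduction is 35 - 7 = 28 and 36 - 8 = 28 days on the first reading, and 34 - 7 = 27 and 35 - 8 = 27 days on the second.

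**With a 7-day limit counted back from enrollment instead.** The 7-day delay to conditioning still adds on. The maximum is then 7 + 7 = 14 and 15 days on the first reading, and 13 and 14 days on the second. The limit should therefore be tied to Day -8.

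**Comparison.** Staging may be at most 14 + 7 = 21 days old at the start of conditioning.

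**Search for a safeguard elsewhere.**
- Day -8 history and examination (10.1.2) is not a test.
- Contraception wording for clofarabine (7.1.4) covers the treatment period and is not a test.
- Pregnancy reporting (7.5) applies after exposure.
- A 1-week pregnancy test before starting therapy appears in 7.1.8, but only for mycophenolate. Under 5.2.2 and 6.2 that drug replaces methotrexate after transplant, so the wording does not govern the first uproleselan or chemotherapy dose.

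No provision in the protocol requires a test between enrollment and Day -8.

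**The case against.** Section 3, Table 8 and exclusion 3.2.8 agree with one another, so this is a design choice and not an internal error, and renal, cardiac, hepatic and lung tests share the same 28 days. The 34 to 36 days is a ceiling that needs the earliest permitted test and the latest permitted start. A beta-HCG drawn with the staging work-up would be at most 21 days old when conditioning starts. The group at risk is small: at most 28 patients, at least 20 of them under 18 (7 + 7 + 6 under 3.1.1), all after at least two cycles of chemotherapy. A pregnancy found before enrollment would still exclude the patient. Many centers probably retest by local practice, and consent forms, which are not available here, may carry further advice. The 7-day limit for conditioning has no direct source in the protocol.

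Most of this stands as a limit on size. It does not close the gap. Nothing requires the beta-HCG to be drawn with staging, and a multicenter protocol should not leave its own exclusion to unwritten local practice. Consent wording would not change the windows in Section 3 and Table 8. Unlike a slow change in organ function, pregnancy status can change completely within the window. The choice of 7 days is a judgement. It matches the protocol's window for weight and its 1-week wording for mycophenolate, but neither dictates it.

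**Conclusion.** The concern holds. The stated windows permit a negative pregnancy test 34 to 35 days old at the first uproleselan dose and 35 to 36 days old at the first chemotherapy, and nothing requires a retest. These are maxima: they assume both windows are used in full, and each range reflects the two readings of when conditioning starts. The number of patients affected cannot be derived from the protocol. No estimate, error rate or sample size is affected. This is a participant-safety weakness that should be corrected, and it is cheap to correct.

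**What to change.** Add to the Section 3 exceptions, and as a Table 8 footnote: females of childbearing potential need a negative serum beta-HCG within 7 days before the first uproleselan dose (Day -8), with the result known before dosing. The eligibility test stays before enrollment. If it is older than 7 days at Day -8, repeat it on a separate serum sample taken with the admission or pre-conditioning bloods. The Table 7 Day -8 draw should not be used, because it is a sodium citrate PK tube taken immediately before the dose, too late for a result.

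The cost is one protocol line, one footnote and one routine blood test in each patient of childbearing potential whose eligibility test is more than 7 days old. That could be most of them, since enrollment alone may precede conditioning by 7 days and registration review takes 48 hours (4.3), but the total remains a subset of at most 28. Two limits remain: a positive result may surface close to admission, and a conception too recent to detect would still be missed.
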